### **Laboratory parameters**

The summary of laboratory evaluations will be presented with respect to three groups of laboratory tests (hematology, serum chemistry, and urinalysis).

- Hematology parameters: hemoglobin, hematocrit, platelet count, red blood cell count (RBC), mean cell volume (MCV), mean cell hemoglobin concentration (MCHC), RBC morphology, white blood cell count (WBC) and differential white blood cell counts.
- Serum chemistry parameters: non-fasting glucose, creatinine, serum urea, uric acid, total protein, SGOT (AST), SGPT (ALT), alkaline phosphatase, sodium, potassium, chloride, phosphorus, magnesium, albumin, total bilirubin, gamma-glutamyl transpeptidase (GGT), calcium; and Glomerular Filtration Rate (GFR).
- Urinalysis parameters: amorphous crystals, urine bilirubin, urine blood, calcium oxalate crystals, urine color, urine glucose, urine ketone, urine leukocytes, urine

nitrite, pH, urine protein dipstick, specific gravity, urine urobilinogen, and WBC Casts (Urine) /LPF.

GFR will be calculated using the Schwartz equation at all visits where serum creatinine will be measured (Visits 9, 10, 12, 13 and 15) by the Central Laboratory.

$GFR (mL/min/1.73 m^2) = k[Height (m)]/Serum Creatinine (mg/dL)$ , where  $k=0.41$

Descriptive summary statistics for both baselines, each post-baseline visit, and change from both baselines to each visit will be presented by laboratory test group and core treatment group. Note that if either the baseline or the post-baseline value is missing, then the calculation of change from baseline will also be missing.

Also, shift tables for hematology and serum chemistry will be provided in order to compare a patient's baseline laboratory evaluation relative to each study visit. For the shift tables, the normal laboratory values will be used to evaluate whether a particular laboratory test value is normal, low, or high for each visit value relative to whether or not the baseline value is normal, low, or high. These summaries, including changes from both baselines, will be presented by laboratory test group and core treatment group.

In addition, summary tables will be presented based on both baselines for the incidence rates of newly occurring clinically notable laboratory abnormalities, where patients will be counted if they have normal or missing baseline value and with at least one post-baseline assessment satisfying the clinically notable criteria. Incidence rates of newly occurring hypocalcemia (based on central lab) by visit will be summarized similarly for patients who have normal or missing baseline level of serum calcium and clinically notable abnormal serum calcium level at each scheduled post-baseline visit. The definition of clinically notable laboratory abnormalities can be found in Appendix section "Clinically notable laboratory values and vital signs" in the protocol.

Furthermore, summary tables will be provided for the number and percentage of patients with liver enzyme abnormalities by each study visit and with at least one post-baseline assessment satisfying the liver enzyme abnormalities compared against both baselines.

Listings of all laboratory parameter measurements will be displayed. The abnormal value will be flagged, e.g., L/H for a value being below/above normal range, and the lower and upper limit of normal values will be presented as well. Central lab calcium values will also be listed for patients with at least one post-baseline laboratory signal of hypocalcemia and the below normal serum calcium results will be flagged as L.

For each numerical laboratory parameter, the number of decimal places to be used for laboratory values should be the same as that for the normal range. For continuous variables recorded as *<lower limit>*, these will be imputed as being half of the lower limit.

All laboratory parameters will be expressed using SI units.

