9.4 Analysis of the primary variable(s)

9.4.1 Variable

This study is designed to observe the long-term safety of zoledronic acid in pediatric patients who were treated with GCs and completed the Core study CZOL446H2337 (Group 1) and those who were not enrolled onto Core study due to symptomatic vertebral fracture but enrolled in this Extension study CZOL446H2337E1 (Group 2). Particular attention will be given to general safety and renal safety.

All safety evaluations will be performed separately using SAF-1 and SAF-2. The assessment of safety will be based mainly on the frequency of adverse events, serious adverse events and on the number of laboratory values that fall outside of pre-determined ranges. Other safety data (e.g. vital signs and special tests) will also be reported.

Adverse events and serious adverse events will be summarized by presenting the number and percentage of patients in which events occur, by primary system organ class, preferred term, and severity. If a patient reports more than one adverse event with the same preferred term, the adverse event with the greatest severity will be presented. If a patient reports more than one adverse event within the same primary system organ class, the patient will be counted only once with the greatest severity. Death, serious adverse events, adverse events causing permanent discontinuation of study drug, and adverse events causing concomitant medication taken will be presented by the core treatment group.

Laboratory data will be presented with respect to three groups of laboratory tests (hematology, serum chemistry, and urinalysis).

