		13 yrs/male	(50.0, 84.0)	If within the normal range at baseline, a value outside of normal range along with at least a 15 unit change
		14 yrs/male	(50.0, 85.0)	If within the normal range at baseline, a value outside of normal range along with at least a 15 unit change
		15 yrs/male	(50.0, 86.0)	If within the normal range at baseline, a value outside of normal range along with at least a 15 unit change
		16 yrs/male	(50.0, 87.0)	If within the normal range at baseline, a value outside of normal range along with at least a 15 unit change
		17-20 yrs/male	(50.0, 89.0)	If within the normal range at baseline, a value outside of normal range along with at least a 15 unit change
		12 yrs/female	(50.0, 82.0)	If within the normal range at baseline, a value outside of normal range along with at least a 15 unit change
		13 yrs/female	(50.0, 84.0)	If within the normal range at baseline, a value outside of normal range along with at least a 15 unit change

Laboratory parameter	Units	Age/gender range	Normal range	Criteria for clinically significant change
		14 yrs/female	(50.0, 85.0)	If within the normal range at baseline, a value outside of normal range along with at least a 15 unit change
		15 yrs/female	(50.0, 86.0)	If within the normal range at baseline, a value outside of normal range along with at least a 15 unit change
		16 yrs/female	(50.0, 86.0)	If within the normal range at baseline, a value outside of normal range along with at least a 15 unit change
		17-20 yrs/ female	(50.0, 86.0)	If within the normal range at baseline, a value outside of normal range along with at least a 15 unit change
Heart Rate	bpm	< 12 yrs	(70.0, 130.0)	If within the normal range at baseline, a value outside of normal range along with at least a 15 unit change
		≥ 12 yrs	(50.0, 120.0)	If within the normal range at baseline, a value outside of normal range along with at least a 15 unit change
Clinical Chemistry				
Blood Urea Nitrogen (serum urea)	mg/dL	≤ 20 yrs	(4.0, 24.0)	Outside the normal range
Calcium	mg/dl	> 2 - 20 yrs	(8.4, 10.3)	Outside the normal range
Chloride	mEq/L	≤ 20 yrs	(94.0, 112.0)	Outside the normal range
Creatinine	mg/dl	5 - 7 yrs/ Female	(0.2, 0.5)	Outside the normal range
		> 7- 10 yrs/ Female	(0.2, 0.6)	Outside the normal range
		> 10 - 13 yrs/ Female	(0.3, 0.7)	Outside the normal range
		> 13 - 16 yrs/ Female	(0.4, 0.8)	Outside the normal range
		> 16 - 20 yrs/ Female	(0.5, 0.9)	Outside the normal range
		5 - 7 yrs/ Male	(0.2, 0.5)	Outside the normal range

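### The SAP's rate of newly occurring notable creatinine mixes low with high values, omits children with a low baseline and ignores the size of a rise, so it is a weak component of the renal safety readout.

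*SAP*

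**What the plan says.** Safety is the primary objective. Protocol 9.4.1 states "Particular attention will be given to general safety and renal safety" and rests the assessment mainly on adverse events, serious adverse events and "on the number of laboratory values that fall outside of pre-determined ranges". Section 3.6 names renal injury as a known risk of the drug.

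The notable limits are in Protocol Appendix 1, Table 13-1. For creatinine, the criterion in every age and sex band is "Outside the normal range". It applies in both directions and needs no change from the child's own baseline. GFR has no row. In the same table, blood pressure and heart rate carry a minimum change, and magnesium is notable only when low.

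The SAP (Laboratory parameters) then limits who enters the incidence table: "patients will be counted if they have normal or missing baseline value and with at least one post-baseline assessment satisfying the clinically notable criteria". The table is run against both the core and the extension baseline. Protocol 9.4.1 also describes a count of patients with notable values after the first dose, but without any condition on baseline.

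**The concern.** The renal question is whether creatinine rises in individual children after an infusion. This incidence rate answers something else, in three ways.

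- **Direction.** A value below the lower limit counts the same as one above the upper limit, although only a rise bears on renal injury.
- **Who can be counted.** A child whose baseline is below range cannot enter the table against that baseline, even if creatinine later exceeds the upper limit. Low values are plausible where muscle mass is low, and Duchenne muscular dystrophy is a named condition in this trial.
- **Size of change.** The limits are wide relative to the values, so creatinine can double inside them and the child is never counted.

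A similar rate in the two core treatment groups could therefore be read as renal reassurance that the rate cannot give.

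**Working it through.** The plan states no detection rate or threshold for this rule, so there is no figure to reproduce. The check is arithmetic on the creatinine limits in Table 13-1.

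**Formula.** The Schwartz equation (Protocol 6.5.4.2; SAP, Laboratory parameters) makes GFR proportional to height divided by creatinine. At constant height, GFR after / GFR before = creatinine before / creatinine after, whatever constant or height unit is used. With lower limit L and upper limit U:

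- largest rise inside the range = U/L
- largest GFR fall inside the range = 1 − L/U
- a halving goes uncounted when baseline ≥ L and 2 × baseline ≤ U, so for baselines from L to U/2

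The limits themselves are taken as in range.

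| Age, sex | L to U (mg/dL) | U/L | 1 − L/U | Baselines where a halving is uncounted |
|---|---|---|---|---|
| 5-7, both | 0.2 to 0.5 | 2.5 | 60% | 0.20 to 0.25 |
| >7-10, girls | 0.2 to 0.6 | 3.0 | 67% | 0.20 to 0.30 |
| >7-10, boys | 0.3 to 0.6 | 2.0 | 50% | 0.30 only |
| >10-13, both | 0.3 to 0.7 | 2.33 | 57% | 0.30 to 0.35 |
| >13-16, both | 0.4 to 0.8 | 2.0 | 50% | 0.40 only |
| >16-20, both | 0.5 to 0.9 | 1.8 | 44% | none (2 × 0.5 = 1.0 > 0.9) |

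Counting each sex separately gives 10 bands. A halving can go uncounted in 8 of them. In three of the 8 (boys >7-10 and both sexes >13-16) only the exact move from L to U escapes. If a value equal to a limit were treated as outside, those three would drop out and 5 would remain.

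**Low baseline.** A 14-year-old going from 0.3 to 0.9 mg/dL (range 0.4 to 0.8) loses 1 − 0.3/0.9 = 67% of GFR and ends above range. A 17-year-old going from 0.4 to 1.0 (range 0.5 to 0.9) loses 1 − 0.4/1.0 = 60%. Neither is newly notable against that baseline.

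**Wrong direction.** A 14-year-old falling from 0.4 to 0.3 is counted, although GFR rises by 0.4/0.3 − 1 = 33%.

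**Age bands.** The SAP does not say whether the range follows age at the visit or at baseline. If it follows age at the visit:

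- An unchanged 0.3 becomes notable on passing from >10-13 to >13-16, and an unchanged 0.4 on passing from >13-16 to >16-20. This applies to both sexes.
- The upper limit also moves up. A rise from 0.3 to 0.8 across the first boundary (0.8/0.3 = 2.67-fold) or from 0.4 to 0.9 across the second (0.9/0.4 = 2.25-fold) is not flagged.

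**The case against.** The strongest reply is that the rate is one output among several, and the others see much of what it misses.

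- The SAP's chemistry shift tables classify baseline and each visit as low, normal or high. They separate high from low and show a low-to-high move.
- Creatinine and GFR changes from both baselines are summarised with minimum and maximum, so the worst change at each visit would appear. Listings show every value with separate low and high flags.
- A renal adverse event search with a Cox model is planned. Protocol 7.1 asks investigators to review significant changes from baseline or the previous visit.
- The incidence table uses both baselines, so a child who is low at one may still enter against the other.
- The primary analysis is descriptive, and no decision depends on this rate.
- Uncounted halvings start from a high GFR. With heights of 100 to 175 cm (an assumption) and height read in cm, GFR at the upper creatinine limit is about 66 to 98 mL/min/1.73 m² (for example 0.41 × 145/0.9 = 66), above the protocol's entry cut-off of 60.
- Protocol 6.5.4.2 withholds the Visit 9 infusion when local creatinine is below range. Taken literally, that would reduce the number of low extension baselines. However, Section 4.2 excludes Group 1 values above range at that visit, so the two texts must be reconciled. The rule also concerns a local test, not the central or core baseline.

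Most of this stands, and it limits the point. It does not correct the incidence rule. Shift tables cannot show a doubling from normal to normal. Extremes and listings give no count. An adverse event requires a report, and Protocol 7.1 treats a laboratory value as one only if it causes symptoms, is judged clinically significant or needs therapy.

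A reader might go further and infer that the renal readout as a whole would miss a halved GFR, or that low-baseline children are removed from the data. The documents do not support either: those children stay in the shift tables, summaries and listings. Nor is a tripling inside the range general. It is possible in one band of ten, between that band's two limits.

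**Conclusion.** The point holds for the newly occurring notable creatinine rate. That rate pools low with high, leaves out low-to-high rises, and has no within-patient change term. A halving of GFR from a baseline at or near the lower limit can go uncounted in 8 of 10 bands, all at ages up to 16. Within the >16-20 bands a halving from a normal baseline is always flagged. The visible text plans no count of children by size of creatinine rise or GFR fall. The SAP's baseline condition also differs from the count described in Protocol 9.4.1.

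This rests on constant height, on limits counted as in range, and, for the age-band effect only, on ranges that follow age at the visit. The documents do not give the number of children with a low baseline creatinine, so the number affected cannot be stated. Redacted safety items and the Laboratory Manual's alert values were not available and are not treated as missing. The change is worth making because renal safety is singled out and the data are already collected. It does not put the primary assessment as a whole in doubt.

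**What to change.** These changes affect SAP reporting only, not patient care.

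1. Report newly high and newly low creatinine separately, and use only newly high as the renal signal.
2. Define newly high as not high at baseline, so that low-baseline children are included. Show children with a missing baseline on their own line. Reconcile this with the unrestricted count in Protocol 9.4.1, and state which age selects the reference range.
3. Add one table by core treatment group: number and percentage of patients with any post-baseline central creatinine (Visits 10, 12, 13, 15) at least 2 times the extension baseline, which at constant height is a Schwartz GFR fall of at least 50%. Include the distribution of each child's maximum ratio. Compute the ratios from unrounded central laboratory values.

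The cost is SAP wording and one extra table. Any ratio cut-off is conventional, and ratios are noisy at low creatinine. If values were rounded to 0.1 mg/dL, a recorded 0.2 to 0.4 could be a true rise of only 0.35/0.25 = 1.4-fold. That is why unrounded values and the full distribution are needed.

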 - [Table 5-1](#) has been revised in line with the current minimum RDAs for vitamin D and calcium from the Institute of Medicine.
 - Visit 9 for Group 1 is now defined as up to 10 months after Visit 5 (month 6) of the Core study, to allow patients who are deteriorating at the time of the second infusion during the Core study to enter the Extension study rather than be treated off-label.
 - This amendment includes clarification of the list of eligible medical conditions other than chronic rheumatologic conditions or inflammatory bowel disease or Duchenne muscular dystrophy (DMD) already specified previously. These additional conditions are listed in [Appendix 6](#) and the exclusion criteria for Group 2 have been revised to address these as follows:
 - Due to the inclusion of some of these additional medical conditions, e.g. nephrotic syndrome, the exclusion criterion of renal impairment previously defined as an estimated glomerular filtration rate (GFR) < 35 mL/min/1.73 m² at screening has been increased to normal renal function defined as < 60 mL/min/1.73 m² based on the Schwartz formula at Visit 8 (Group 1) or Visit 8A (Group 2).
 - Schwartz formula has been added under [Section 6.5.4.2](#)
 - In addition ‘serious renal disease’ in DMD has been removed as this is included under the GFR exclusion criterion.
 - In DMD patients, chronic muscle breakdown results in elevated aspartate aminotransferase (AST) and alanine aminotransferase (ALT) (frequently higher than 10 fold); hence total bilirubin and gamma-glutamyl transpeptidase (GGT) have been added as additional markers to detect any potential liver toxicity.

- The exclusion criterion ‘symptomatic cardiac abnormality’ in DMD has been redefined because other conditions or concomitant medications, including glucocorticoids can contribute to cardiac disease: Uncontrolled symptoms of cardiac failure or arrhythmia.
- Serum 25-hydroxy vitamin D concentrations have been revised to the currently accepted definition of normal i.e. < 20 ng/mL or < 50 nmol/L at Visit 8A for Group 2.
- The blood volume required ([Appendix 7](#)) for the analysis of specialized bone markers has been reduced from 8.5 mL to 3 mL.
- The local serum creatinine before the second infusion of zoledronic acid has been removed because of the need for normal renal function as an eligibility criterion. Renal function is reviewed centrally before and 10 days after each infusion.

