Summary statistics (means, medians, standard deviations, ranges) of raw data and change from baseline values) will be presented. In addition, shift tables using extended normal ranges (baseline to post-baseline value) will be provided in order to compare a patient's baseline laboratory evaluation relative to each study visit. For the shift tables, the normal laboratory values will be used to evaluate whether a particular laboratory test value is normal, low, or high for each visit value relative to whether or not the baseline value is normal, low, or high. These summaries will be presented by laboratory test and by the core treatment group. For Group 1, both changes from Baseline 1 (first visit of the Core) and Baseline 2 (first visit of the Extension) will be reported. The number and percentage of patients who have lab values that meet the criteria for being clinically notable after the first dose of study medication will be presented by the Core treatment group. Patient listings that present each patient's lab profile for those tests that are outside of the clinically notable ranges will also be provided.

The ranges of the normal laboratory values as well as the alert values for the safety monitoring will be provided in the Laboratory Manual, which will be attached to the protocol as an exhibit.

Data from other assessments (e.g. vital signs) will be listed, notable values will be flagged, and any other information collected will be listed as appropriate. The number and percentage of patients who have vital sign values that meet the criteria for being clinically notable after the first dose of study medication will be presented by the Core treatment group. Any statistical tests performed to explore the data will be used only to highlight any interesting comparisons that may warrant further consideration.

No statistical test will be performed for Group 2.

Details will be available in statistical analysis plan.

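### The planned ALT/AST counts use one 200 U/L limit for all children and require a normal or missing baseline, so they can miss worsening in Duchenne patients and most five-fold rises in the others

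*SAP*

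**What the plan says.** Protocol section 9.4.1 rests the primary safety assessment mainly on adverse events, serious adverse events and "on the number of laboratory values that fall outside of pre-determined ranges". For liver enzymes, Table 13-1 (Appendix 1) gives one range for ages 5–20, both sexes and every disease: ALT 6–200 and AST 10–200 U/L. A value outside the range is notable. The GGT limits in the same table vary by age and sex.

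The Amendment 3 rationale explains that in DMD "chronic muscle breakdown results in elevated aspartate aminotransferase (AST) and alanine aminotransferase (ALT) (frequently higher than 10 fold"), and that total bilirubin and GGT "have been added as additional markers to detect any potential liver toxicity".

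Three counts could use these limits:

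- **Protocol 9.4.1** counts "patients who have lab values that meet the criteria for being clinically notable after the first dose of study medication". It states no baseline condition and leaves details to the SAP.
- **SAP, Laboratory parameters**, newly occurring notable abnormalities, against both baselines: "patients will be counted if they have normal or missing baseline value and with at least one post-baseline assessment satisfying the clinically notable criteria". For the criteria it points to the protocol: "The definition of clinically notable laboratory abnormalities can be found in Appendix section", meaning Appendix 1.
- **SAP, same section**: "summary tables will be provided for the number and percentage of patients with liver enzyme abnormalities by each study visit", and for any post-baseline assessment, compared against both baselines. No numerical criterion is given.

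The SAP presents laboratory tables by core treatment group. Under Adverse events it plans one table by underlying disease group, but no laboratory table has that split.

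**The concern.** A notable limit is useful if a child without a drug effect is usually below it and a child with a drug effect usually crosses it. By the protocol's own account, many DMD children would be above 200 U/L before the first extension infusion. The baseline condition then removes them from the newly notable count, so a further rise cannot register there. In children without DMD the same limit is several times a usual upper limit of normal, so a clear rise can stay below it.

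At stake is whether the ALT/AST counts, one component of the primary safety summary, can register hepatocellular change in either group. With both groups pooled, a reader also cannot tell whether a counted child crossed the limit because of muscle disease.

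**Working it through.** The plan states no operating figure for these counts, so there is none to reproduce.

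**Inputs from the documents.** Upper limit 200 U/L (Table 13-1). Baseline rule and at-least-one-post-baseline rule (SAP, Laboratory parameters). Two post-dose ALT/AST measurements, Visits 12 and 15, because Visits 10 and 13 carry only a renal and electrolyte panel (protocol Appendix 7).

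**Assumptions, not in the documents.** Log-normal ALT. DMD median 300–450 U/L, which is 10 × an upper limit of 30–45; between-child log-SD 0.4–0.7. Non-DMD median 15–30 U/L; between-child log-SD 0.35. Within-child log-SD 0.25 in both groups. A normal baseline is read as one inside the Table 13-1 range.

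**Step 1: the limit as a multiple of a usual upper limit.** 200/50 = 4.0, 200/40 = 5.0, 200/30 = 6.7.

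**Step 2: DMD children shut out at baseline.** The share above 200 is Φ[ln(M/200) / √(σ_b² + σ_w²)].

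- M = 300, σ_b = 0.7: ln 1.5 = 0.405; √(0.49 + 0.0625) = 0.743; Φ(0.545) = 0.71.
- M = 450, σ_b = 0.4: ln 2.25 = 0.811; √(0.16 + 0.0625) = 0.472; Φ(1.72) = 0.96.

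**Step 3: DMD counts with no drug effect.** Simulated with one baseline and two post-dose values:

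| Median (U/L) | σ_b | Above 200 at baseline | Above 200 at least once post-dose | Newly notable |
|---|---|---|---|---|
| 300 | 0.4 | 81% | 89% | 11% |
| 300 | 0.7 | 71% | 77% | 10% |
| 400 | 0.4 | 93% | 97% | 5% |
| 400 | 0.7 | 82% | 87% | 7% |
| 450 | 0.4 | 96% | 98% | 3% |
| 450 | 0.7 | 86% | 90% | 6% |

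The newly notable share cannot exceed 100% minus the share above 200 at baseline, so its ceiling is 4–29% whatever the drug does.

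**Step 4: a count with no baseline condition.** If 200 U/L were used without the baseline rule, 77–98% of DMD children would be flagged with no drug effect. At σ_b = 0.5, a true doubling of ALT would move that share only from 84% to 99% (median 300) or from 94% to 99.8% (median 400).

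**Step 5: non-DMD, sustained five-fold rise.** The typical value reaches 5 × 15 = 75, 5 × 20 = 100 or 5 × 30 = 150 U/L, all below 200. With two visits and within-child variation, 2.0%, 8.7% and 35.8% are counted.

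**Sensitivity.**

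- DMD median 300–500 with within-child log-SD 0.2–0.4: 69–98% shut out, about 1.5–17% newly notable.
- DMD median 200: about half shut out, and 58–62% above 200 at least once (within-child log-SD 0.25).
- If a normal baseline means about 40 U/L or less, DMD entry to the newly notable count is about 0%.
- Non-DMD medians 20–25, between-child log-SD 0.4, within-child 0.2–0.4: 9–32% counted at five-fold and 40–67% at eight-fold.

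**The case against.** The strongest reply is that these counts are one view among several. The SAP also gives change from both baselines and shift tables for chemistry, and lists every value with flags and normal limits. Clinically significant laboratory values are reportable as adverse events, which are tabulated by disease group. GGT and total bilirubin are in the panel and in Table 13-1, so the markers added because of DMD do enter the notable counts. The safety analysis is descriptive, with no liver test or decision rule. All of this stands, and it limits the point to the ALT/AST counts. The shift tables help less than they seem to: a child already high stays high, and the protocol refers to extended normal ranges where the SAP refers to normal laboratory values.

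A reader might infer that the liver counts mainly track DMD muscle breakdown, or that DMD imbalance between core arms would look like a liver signal. The documents do not support that. The SAP's newly notable count removes most such children. The liver-enzyme table states no 200 U/L criterion and is set against both baselines. The protocol count with no baseline condition defers to the SAP. The SAP also calls underlying condition a stratification factor, which limits chance imbalance between the core arms; selective continuation into the extension is possible, but nothing in the documents shows it. Flagging most DMD children regardless of drug therefore remains conditional on how those two counts are programmed.

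It is also fair that the DMD share, the ALT distribution and the laboratory's upper limits are not given. The protocol says frequently, not always, and does not say what the 10-fold is relative to.

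**Conclusion.** The point holds for the ALT/AST counts. As written, a DMD child above 200 U/L at baseline cannot be newly notable on that enzyme, and a child without DMD is counted as high only above 200 U/L. Both statements follow from the text without any assumption. Their size does depend on assumptions: about 71–96% of DMD children shut out, 3–11% counted from fluctuation, and about 2–36% of sustained five-fold rises counted in non-DMD children. These percentages are illustrative.

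It would be too strong to say that the plan hides transaminase rises, because summaries and listings still show them; the plan leaves them uncounted. This is worth correcting before the tables are produced, but it does not undermine the safety evaluation as a whole.

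**What to change.** In the SAP section on laboratory parameters:

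1. Present the notable and liver-abnormality tables for ALT, AST, GGT and total bilirubin for DMD and non-DMD separately within core arm.
2. Add an ALT/AST count that works when baseline is abnormal, as the ratio to the child's own extension baseline (for example at least 2×). In DMD, read it together with GGT and bilirubin.
3. For non-DMD children, define liver enzyme abnormalities by multiples of the central laboratory's upper limit (for example above 3× and above 5×), alongside the 200 U/L count. State the criterion used in the DMD table as well.
4. State which range makes a baseline normal, and use the same range in the shift tables.

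These are analysis and reporting criteria only. The laboratory values and underlying condition are already collected, so the cost is SAP wording and a few more tables. The drawback is small denominators: about 100 patients are planned across both groups, and the DMD share is not stated.
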